6.5.3. Prohibited Medications

Participants **must not initiate** any of the following prohibited medications:

- Immunomodulatory non-biologic agents other than 6-MP, AZA, or MTX (including but not limited to 6-TG, cyclosporine, tacrolimus, sirolimus, mycophenolate mofetil, tofacitinib, and other JAK inhibitors)
- Immunomodulatory biologic agents (including but not limited to TNF α antagonists, natalizumab, vedolizumab, and ustekinumab)
- Experimental Crohn's disease medications

Because protection of human research participants is paramount, it is recognized that initiating such therapies may be required due to medical necessity. However, initiation of these prohibited medications should be documented as a deviation from the study protocol, and the participant will be discontinued from receiving further study intervention.

Participants must not enroll in any other clinical study with an investigational agent while in this study and must terminate study participation if they do. A participant who intends to enroll in any other clinical study with an investigational agent should undergo an early termination visit before he or she withdraws from study participation.

The sponsor must be notified in advance (or as soon as possible thereafter) of any instances in which prohibited therapies are administered.

6.6. Dose Modification

Dose modification is not permitted in this intervention cohort.

6.7. Study Intervention After the End of the Study

Investigators may recontact the participant to obtain long-term follow-up information regarding the participant's safety or survival status as noted in the ICF (refer to Informed Consent in Appendix 5 of the Master protocol PLATFORMPACRD2001, Regulatory, Ethical, and Study Oversight Considerations).

Participants will be instructed that study intervention will not be made available to them after they have completed/discontinued the study intervention and that they should return to their primary physician to determine standard of care.

7. DISCONTINUATION OF STUDY INTERVENTION AND PARTICIPANT DISCONTINUATION/WITHDRAWAL

7.1. Discontinuation of Study Intervention

Participants will not be automatically withdrawn from the study if they discontinue the study intervention before the end of the dose regimen.

A participant's study intervention must be discontinued if:

- The participant withdraws consent to receive study intervention.
- The investigator believes that for safety reasons or tolerability reasons (eg, an AE) it is in the best interest of the participant to discontinue study intervention.
- The participant becomes pregnant. Refer to [Appendix 2](#) of this ISA, Contraceptive and Barrier Guidance and Collection of Pregnancy Information.
- The participant is deemed ineligible according to the following TB screening criteria:
 - A diagnosis of active TB is made.
 - A participant has symptoms suggestive of active TB based on follow-up assessment questions and/or physical examination or has had recent close contact with a person with active TB, and cannot or will not continue to undergo additional evaluation.
 - A participant undergoing evaluation has a chest radiograph with evidence of current active TB and/or a positive QuantiFERON®-TB test result and/or an indeterminate QuantiFERON®-TB test result on repeat testing (refer to Section [5.2](#) of this ISA); and/or a positive tuberculin skin test result in countries in which the QuantiFERON®-TB test is not approved/registered or the tuberculin skin test is mandated by local health authorities.
- The participant develops an opportunistic infection, ie, an infection by an organism that usually causes disease only in a host whose resistance is lowered (eg, *Pneumocystis jirovecii*, *coccidioidomycosis*, *Mycobacterium avium*).

- The participant develops a malignancy including squamous cell skin cancer. Consideration may be given to allow participants who develop ≤ 2 basal cell skin cancers that are adequately treated with no evidence of residual disease to continue to receive study agent.
- The participant initiates any of the following protocol-prohibited medications at any time during the study:
 - Immunomodulatory agents other than AZA, 6-MP, or MTX (including, but not limited to, 6-TG, cyclosporine, mycophenolate mofetil, tacrolimus, and sirolimus).
 - Immunomodulatory biologic agents (including, but not limited to, TNF antagonists, abatacept, anakinra, rituximab, vedolizumab, natalizumab, ustekinumab).
 - Experimental Crohn's disease medications (including, but not limited to, tofacitinib, etrolizumab, guselkumab, risankizumab, brazikumab, or other experimental anti-IL-23 agents).
 - Thalidomide or related agents.
- The participant has any Crohn's disease-related surgeries that represent a lack of efficacy of study agent or will preclude the future ability to assess efficacy through the CDAI
 - Other permitted Crohn's disease-related surgeries (eg, to resolve long-standing complications such as strictures or for symptomatic nonhealing fistulas, in participants experiencing improvement on the study intervention) other than minor procedures (eg, placement of a seton or cutaneous drainage of an abscess) should be postponed until after the Week 12 visit, unless necessary to ensure the participant's well-being and/or safety.
- The participant develops severe hepatic function abnormalities, as described in Section [8.2.4](#) and [Appendix 4](#), Liver Safety: Suggested Actions and Follow-up Assessments, both of this ISA
- Adverse events of National Cancer Institute Common Terminology Criteria for Adverse Events (NCI-CTCAE) grade ≥ 3 will be evaluated by the investigator and the study medical monitor to make a determination on discontinuation of the study intervention. Discontinuation of the study intervention should be considered in participants with worsening Crohn's disease where continuation of the study drug is not in the best interest of the participant.
- Total (complete) or partial (supplemental) parenteral nutrition is initiated through an indwelling catheter at any time during the study.
- A participant has symptoms of anaphylaxis, such as bronchospasm with wheezing and/or dyspnea that requires ventilatory support OR that results in symptomatic hypotension with a decrease in systolic blood pressure >40 mm Hg or blood pressure $<90/60$ mm Hg following study intervention administration. This may include events of NCI-CTCAE toxicity grade ≥ 3 .
- A participant has a serious adverse allergic reaction that is possibly related to the study intervention.
- The participant (or the participant's representative) withdraws consent for administration of the study intervention.

In the event of any serious infection, the intervention must be held and may not be resumed until the investigator has discussed the case with the study medical monitor.

Study intervention assigned to the participant who discontinued study intervention may not be assigned to another participant. Additional participants will not be entered to ensure the protocol-specified number of participants complete the study.

Refer to Section 7.1 of the Master protocol PLATFORMPACRD2001 for additional considerations for discontinuation of study intervention.

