6.5.1. Rescue Medication

Participants may transiently use (ie, for <4 weeks) increased doses of corticosteroids for reasons other than loss of response to treatment for Crohn's disease (eg, stress doses of corticosteroids for surgery, asthma, adrenocortical insufficiency, etc).

Although enrolled participants should not initiate or increase the dose of oral or rectal 5-ASA compounds, immunomodulators (ie, AZA, 6-MP, or MTX), corticosteroids, or antibiotics as a treatment for Crohn's disease so as not to confound the efficacy assessments, it is recognized that the use of such compounds may be medically necessary. In such cases, participants may continue to receive the study intervention, but would be considered a treatment failure. This would not represent a deviation from the study protocol.

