6.5.2. Crohn's Disease-Specific Therapies

Participants must continue to receive their concomitant, background oral 5-ASA compounds, the immunomodulators AZA, 6-MP, and MTX, oral corticosteroids, and/or antibiotics for the treatment of Crohn's disease during the study (as defined in the inclusion criteria). **Concomitant medications for Crohn's disease at study enrollment should be maintained at a stable dose throughout this study.**

Enrolled participants **should not initiate** any of the following Crohn's disease-specific medical therapies during their participation in the study:

- Oral or rectal 5-ASA compounds
- Immunomodulators (ie, AZA, 6-MP, or MTX)
- Parenteral or rectal corticosteroids
- Antibiotics as a treatment for Crohn's disease
- Total parenteral nutrition as a treatment for Crohn's disease

Because protection of human research participants is paramount, it is recognized that initiating or modifying the dose of the above therapies may be medically required. If the above medications are initiated or medication doses are changed, participants may continue to receive the study

intervention, and should continue to attend all study visits and have all assessments. If due to medical necessity in the opinion of the investigator, the above medications are initiated or medication doses are changed, this does not represent a deviation from the study protocol, but may be considered a treatment failure.

Oral corticosteroid should not be initiated during the study.

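### For total parenteral nutrition started to treat Crohn's disease, Protocol 6.5.2 lets study drug continue while 7.1 requires it to stop; 6.5.2 is the text to correct

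*Protocol*

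**What the plan says.** **Protocol 6.5.2 (Crohn's Disease-Specific Therapies).** The therapies that enrolled participants should not start include oral or rectal 5-ASA, immunomodulators, parenteral or rectal corticosteroids, antibiotics for Crohn's disease, and "Total parenteral nutrition as a treatment for" Crohn's disease. The section then accepts that "initiating or modifying the dose of the above therapies may be medically required". It continues: "If the above medications are initiated or medication doses are changed, participants may continue to receive the study" intervention. Where the change is medically necessary, "this does not represent a deviation from the study protocol, but may be considered a treatment failure".

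**Protocol 7.1 (Discontinuation of Study Intervention).** Under the lead-in that a participant's "study intervention must be discontinued if" any listed condition applies, one item reads: "Total (complete) or partial (supplemental) parenteral nutrition is initiated through an indwelling catheter at any time during the study".

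**Neighbouring protocol text.**
- Section 6.5.3, on prohibited medications, repeats the mandatory stop: "the participant will be discontinued from receiving further study intervention".
- Section 6.5.1 gives a firm failure rule, "In such cases, participants may continue to receive the study intervention, but would be considered a treatment failure", but only for 5-ASA compounds, immunomodulators, corticosteroids and antibiotics.
- Section 4.2.1 says study drug should be stopped when a participant needs additional therapy for Crohn's disease.

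**SAP 5.3.1 and 5.3.2.1.** Treatment failure covers Crohn's disease surgery, discontinuation for lack of efficacy or for an adverse event of worsening Crohn's disease, and a defined list of medication changes in five classes: corticosteroids, 5-ASA, immunomodulators, prohibited medications and antibiotics. Nutrition is not on that list. Intercurrent event category 2 refers only to a prohibited change in Crohn's disease medication.

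**The concern.** Both protocol sections are operative instructions to sites. A site that starts total parenteral nutrition for Crohn's disease through an indwelling catheter and turns to 6.5.2 reads that drug may continue and that nothing need be recorded as a deviation. By following that text it breaches a mandatory stop in 7.1. Section 6.5.3 shows what is missing: it restates the 7.1 stop for its own therapies, and 6.5.2 does not do so for parenteral nutrition.

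There is a secondary consequence for the analysis. The primary estimand assigns the baseline CDAI after treatment failure. Because no failure rule names parenteral nutrition, a participant kept on drug under 6.5.2 would contribute the observed Week 12 score unless another failure rule applied. That score could be affected by the nutrition itself, since body weight and liquid-stool count are CDAI components (SAP 5.3.1 and Attachment 3).

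**Working it through.** **1. Where the two sections overlap.** Section 6.5.2 covers total parenteral nutrition given as Crohn's disease treatment. Section 7.1 covers total or partial parenteral nutrition, for any reason, through an indwelling catheter. The conflict is the intersection: total, for Crohn's disease, through an indwelling catheter. Partial nutrition, and nutrition given for other reasons, fall under 7.1 alone.

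**2. Which section should give way.** Section 7.1 is mandatory and 6.5.2 is permissive, so stopping drug satisfies both. Section 4.2.1 also favours stopping. Section 6.5.2 is therefore the one to amend.

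**3. How the SAP would handle the event, if no other failure rule applies.**
- Drug continued under 6.5.2: no rule names the event, so the observed CDAI is used.
- Drug stopped, coded as lack of efficacy or worsening Crohn's disease: category 3, composite strategy, baseline value.
- Drug stopped, coded as another reason (unusual for this event): category 5, treatment policy, observed value if available.

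**4. The plan's power, reproduced for context.** Inputs are SD 93 and difference 60 (SAP 3), 54 and 36 participants, and two-sided alpha 0.1 (Protocol 9.2.3.2).
- SE of the difference = 93 × √(1/54 + 1/36) = 20.0.
- Power by the normal approximation = Φ(60/20.0 − 1.645) = 91.2%; with a noncentral t on 88 df, 90.8%.
- This agrees with the stated figure of about 90%. Nothing in this point changes these inputs.

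**5. Effect of one participant on the estimate.** The documents give neither an event rate nor a typical CDAI change after parenteral nutrition. I assume an individual change of 50 to 100 points, in either direction. SAP Attachment 3 weights give a sense of scale for a one-step change held for 7 days:
- liquid stools 7 × 2 = 14; abdominal pain 7 × 5 = 35; well-being 7 × 7 = 49;
- stools plus pain = 49; all three = 98.

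This only shows how large 50 to 100 points is. The documents do not link parenteral nutrition to pain or well-being.

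Replacing the observed change by zero (the baseline value) shifts the unadjusted arm mean by change/n:

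| Analysis | Active | Placebo | SE of difference | Shift in SE |
|---|---|---|---|---|
| Final, 54:36 | 50/54 = 0.9 to 100/54 = 1.9 | 50/36 = 1.4 to 100/36 = 2.8 | 20.0 | 0.05 to 0.14 |
| Interim, 27:18 | 50/27 = 1.9 to 100/27 = 3.7 | 50/18 = 2.8 to 100/18 = 5.6 | 93 × √(1/27 + 1/18) = 28.3 | 0.07 to 0.20 |

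The 27:18 split assumes that the approximately 45 interim participants follow the 3:2 allocation.

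**6. Direction.** If the participant improved, the baseline value removes an apparent gain. If the Week 12 CDAI is at or above baseline, which is plausible in someone needing parenteral nutrition, the substitution does nothing or works the other way. The shift also reverses with the arm. The smallest possible effect is therefore zero.

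**The case against.** The best defence is that a permission and a requirement do not strictly collide. Section 7.1 is the dedicated discontinuation section, its item is the more specific, and a careful reader would apply it. Section 6.5.2 also says medications, not therapies, in the sentence that allows drug to continue, which could be read as leaving nutrition out. The first part stands in that following 7.1 satisfies both sections. It does not remove the defect, because no supplied text says which section governs and 6.5.2 tells the site that there is no deviation. The wording argument is weak: the preceding sentence refers to therapies, and total parenteral nutrition is on that list. If it were accepted, nutrition would also fall outside category 2, which speaks of medication.

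On the SAP, most of the defence stands. Once drug is stopped as 7.1 requires, the natural coding is lack of efficacy or worsening disease, and category 3 assigns the baseline value. Accompanying rescue medication on the failure list would trigger failure separately. Protocol 6.5.2 says only that the event may count as failure, so a reader who infers that the SAP contradicts the protocol goes too far.

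A reader might also infer that the primary result is biased. The documents do not support that. Treatment is double-blind, Exclusion 7 removes people expected to need parenteral nutrition through an indwelling catheter, and the individual shift has no fixed sign.

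Two limits remain. The Master protocol, to which 7.1 and the analysis sections refer, was not available and may say more. Section 4.2.1 also sits awkwardly with 6.5.2 for the other listed therapies, so an exception for parenteral nutrition alone does not settle every tension between them.

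**Conclusion.** The conflict is real but narrow. For one defined event, 6.5.2 permits what 7.1 forbids, and 6.5.2 is wrong as written. The main reason to correct it is the stopping rule, since sites need a single instruction. The SAP omission is a secondary consistency matter: it has effect only if a site keeps the participant on drug, or stops it and codes the stop unusually, with no other failure rule triggered.

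Severity is low. The event should be rare, although the documents give no rate. Under the assumed individual change of up to about 100 points either way, the effect is at most about 0.14 standard errors per participant at the final analysis and about 0.20 at the interim. These figures use unadjusted means and the SAP's SD of 93; the planned MMRM could differ slightly. Neither a directional bias nor a loss of power follows. The conclusion is limited to this intervention-specific protocol and this SAP.

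**What to change.** **Protocol 6.5.2.** Except total parenteral nutrition from the sentence that allows study drug to continue, and refer to the mandatory stop in 7.1, as 6.5.3 already does in substance for prohibited medications.

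**SAP 5.3.1 (secondary).** Add initiation of parenteral nutrition for worsening Crohn's disease to the treatment failure list, mapped to intercurrent event category 2, whether or not drug was stopped and whatever reason was coded.

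The cost is one phrase with a cross-reference in the protocol and one line in the SAP. No visits, procedures or participants are added.

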7.2. Participant Discontinuation/Withdrawal From the Study

Refer to Section 7.2 of the Master protocol PLATFORMPACRD2001 for participant discontinuation or withdrawal considerations.

7.3. Lost to Follow-up

Refer to Section 7.3 of the Master protocol PLATFORMPACRD2001 for follow-up considerations.

8. STUDY ASSESSMENTS AND PROCEDURES

Overview

Participants in the JNJ-67864238 intervention cohort will be assessed using the study evaluations described in Section 8 of the Master protocol PLATFORMPACRD2001. Participants will also be assessed using the following JNJ-67864238-specific assessments and procedures.

The Schedule of Activities ([Table 1](#)) summarizes the frequency and timing of efficacy, PK, immunogenicity, PD, biomarker, pharmacogenomic, and safety measurements applicable to this intervention cohort.

Contraception

Women of childbearing potential must have a negative serum β -hCG pregnancy test result at screening as described in the Schedule of Activities ([Table 1](#)). Participants must be reminded that they are required to use a highly effective method of contraception during the study and must continue using contraception as directed after receiving the last administration of the study intervention (Section [5.1](#) of this ISA). The method(s) of contraception used by each participant must be documented. Additional serum or urine pregnancy tests may be performed, as determined necessary by the investigator or required by local regulation, to establish the absence of pregnancy at any time during the participation in the study.

Blood Volume

For each participant, the maximum amount of blood drawn from each participant in this study will not exceed 500 mL.

The total blood volume to be collected is considered to be an acceptable amount of blood to be collected over this time period from the population in this study based upon the World Health Organization's *Blood Donor Selection: Guidelines on Assessing Donor Suitability for Blood Donation*, which state that whole blood donation should not exceed 13% of blood volume (ie,

350 mL \pm 10% for a donor with a body weight of 45 kg and 450 mL \pm 10% for a donor with a body weight of 50 kg). The total blood volume collected in this study is below the amounts recommended for a single blood donation.¹⁴

Repeat or unscheduled samples may be taken for safety reasons or for technical issues with the samples.

8.1. Efficacy Assessments

Refer to Section 8.1 of the Master protocol PLATFORMPACRD2001 for efficacy assessments.

8.2. Safety Assessments

Refer to Section 8.2 of the Master protocol PLATFORMPACRD2001 for safety assessments. Participants in the JNJ-67864238 intervention cohort will also have the safety assessments in the following sections. The study will include the following evaluations of safety and tolerability according to the time points provided in the Schedule of Activities ([Table 1](#)).

8.2.1. Physical Examinations

Physical examination will be performed as indicated in the Schedule of Activities ([Table 1](#)). Clinically significant findings should be reported as AEs.

8.2.2. Vital Signs

Temperature, pulse/heart rate, blood pressure, respiratory rate, and body weight will be assessed.

8.2.3. Electrocardiograms

During ECGs, participants should be in a quiet setting without distractions (eg, television, cell phones). Participants should rest in a supine position for at least 5 minutes before the ECG and should refrain from talking or moving arms or legs. If blood sampling or vital sign measurement is scheduled for the same time point as ECG recording, the procedures should be performed in the following order: ECG(s), vital signs, blood draw.

Electrocardiograms will be performed at screening, Week 12, and the final safety visit.

8.2.4. Clinical Safety Laboratory Assessments

Clinical laboratory assessments will include hematology assessments, blood chemistry assessments, pregnancy testing, serology (HIV antibody; HBV surface antigen [HBsAg; Appendix 4 of the Master protocol PLATFORMPACRD2001, Hepatitis B Virus Screening]; and HCV antibody), and liver function tests ([Appendix 4](#) of this ISA, Liver Safety: Suggested Actions and Follow-up Assessments) for additional information on monitoring and assessment of abnormal liver function tests.

Pregnancy testing (serum or urine) should be conducted as indicated in the Schedule of Activities ([Table 1](#)).

Blood samples for serum chemistry and hematology will be collected as noted in [Appendix 5](#) of this ISA, Clinical Laboratory Tests. The investigator must review the laboratory results, document this review, and record any clinically relevant changes occurring during the study in the Adverse Event section of the CRF. The laboratory reports must be filed with the source documents.

8.2.5. Signs of Infection

The study intervention should not be administered to a participant with a clinically important, active infection. Investigators are required to evaluate participants for any signs or symptoms of infection, and also review participant's diary entries for signs of infection, at scheduled visits in the Schedule of Activities ([Table 1](#)). If a participant develops a serious infection, including but not limited to sepsis or pneumonia, discontinuation of the study intervention (ie, no further study intervention administrations) must be considered.

